9.6 Safety Analyses

9.6.1 Safety Analysis of Low LDL-C

The safety analyses (TEAE and serious TEAE) will be summarized for subjects with any postbaseline LDL-C and all postbaseline LDL-C with the cutoffs of < 25 mg/dL, < 40 mg/dL and ≥ 40 mg/dL for the OLE study period using the OLE safety analysis set. In addition, the safety analyses will be summarized in subjects with 2 consecutive postbaseline LDL-C < 25 mg/dL and LDL-C < 40 mg/dL separated by at least 21 days.

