7.2.2 Treatment

The following procedures will be completed during the 5-year (260 week) treatment period at the times designated in the Schedule of Assessments ([Table 3](#)).

Administration of evolocumab is to be administered after completion of the blood draws and vital signs during each visit that it is required.

- vital signs (eg, sitting blood pressure and heart rate)
- review of adverse events/serious adverse events/adverse device effects/disease-related events
- review of concomitant therapy
- body weight
- **coronary revascularization procedure and death information (sites will be prompted for this information when necessary)**
- blood draws for fasting lipids (\geq 9-hour fasting sample), ApoA1, ApoB, and Lp(a)
- blood draw for a serum pregnancy test (women of childbearing potential only by central laboratory per local institutional standard practice)
- administration of evolocumab at study site (see [Section 6.2.1](#) for instruction and supervision of subjects), if applicable
- reconciliation of used evolocumab, and dispensing evolocumab (prefilled AI/pens or PIs), if applicable

The investigator should instruct the subject to report to the site (eg, by telephone call) any adverse events, serious adverse events, adverse device effects, disease-related events at any time (ie, between scheduled visits). In addition, subjects will be contacted by telephone as designated in the schedule of assessments ([Table 3](#)) for collection of adverse events, serious adverse events, adverse device effects, disease-related events.

If, in the opinion of the investigator, a subject is unable to tolerate evolocumab, that subject will discontinue evolocumab but will continue to return for all other study procedures and measurements through the EOS.

If a subject withdraws from the study early, investigators should make every effort to complete and report the observations as thoroughly as possible up to the date of withdrawal. If possible, the **week 260** procedures should be completed at the time of withdrawal (see [Section 7.2.3](#)).

Vital status must be obtained for all subjects within the limits of local law. This includes subjects who may have discontinued study visits with or without withdrawing consent and should include interrogation of public databases, if necessary. If deceased, the date of death should be obtained and reported.

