3.1 Study Design

This is a multicenter, open-label extension (OLE) study designed to assess the extended long-term safety of evolocumab in subjects who have completed the FOURIER trial (Study 20110118). FOURIER is a randomized placebo-controlled study of evolocumab, in patients with clinically evident atherosclerotic CVD on stable effective statin therapy. Subjects at sites participating in FOURIER OLE (Study 20160250) who are eligible and have signed the FOURIER OLE informed consent will be enrolled after completion of FOURIER.

The FOURIER OLE study requires laboratory assessments at day 1, week 12, and thereafter approximately every 6 months from day 1; the corresponding blood samples will be processed using a central laboratory.

Upon enrollment in FOURIER OLE study, subjects will receive evolocumab 140 mg every 2 weeks (Q2W) or 420 mg monthly (QM) according to their preference. Frequency and corresponding dose of administration can be changed at any scheduled time point where evolocumab is supplied to the subject, provided the appropriate supply is available. It is recommended that subjects continue the same background lipid-lowering therapy (LLT), including statin, as taken during FOURIER.

This study will continue for 260 weeks (approximately 5 years). Subjects ending administration of evolocumab should continue study assessments until the end of study.

All subjects will be followed and complete procedures/assessments from enrollment through the date of study termination unless the subject has withdrawn consent, irrespective of whether the subject is continuing to receive treatment. All deaths and cardiovascular events of interest will be reviewed by an independent external Clinical Events Committee (CEC), using standardized definitions.

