5.3 Other Study Related Definitions

Treatment-emergent adverse event

Events are categorized as Adverse Events (AEs) or **Disease-related Events (DREs)** starting on or after first dose of investigational product as determined by the flag indicating if the event started prior to the first dose on the Events eCRF and up to the EOS/Safety Follow-up visit or 30 days after the last administration of evolocumab, whichever is earlier.

Treatment-Emergent Disease-Related Events

Events categorized as Disease-related Events (DREs) defined in Protocol Section 9.1.1 starting on or after first dose of investigational product as determined by the flag indicating if the disease-related event started prior to the first dose on the Events eCRF and up to the EOS/Safety Follow-up visit or 30 days after the last administration of evolocumab, whichever is earlier.

Analytical Study Week Assignments

Analytical windows will be used to assign parameters to study weeks. The algorithm is provided in [Appendix A](#).

Investigational Product (IP)

Investigational product includes evolocumab 140 mg every two weeks (Q2W) and 420 mg monthly (QM).

IP Exposure Period in Months (Parent study)

For subjects whose last IP dose is Q2W:

IP exposure period = [min(last IP dose date in parent study + 14 days, EOS date) – first IP dose date in parent study + 1] / 365.25 x 12

For subjects whose last IP dose is QM:

IP exposure period = [min(last IP dose date in parent study + 28 days, EOS date) – first IP dose date in parent study + 1] / 365.25 x 12

IP Exposure Period in Months (For OLE period)

For subjects whose last IP dose is Q2W:

IP exposure period in OLE period = [min(last IP dose date in OLE period + 14 days, EOS date) – first IP dose date in OLE period + 1] / 365.25 x 12

For subjects whose last IP dose is QM:

IP exposure period in OLE period = [min(last IP dose date in OLE period + 28 days, EOS date) – first IP dose date in OLE period + 1] / 365.25 x 12

IP Exposure Period in Months (For the combined parent and OLE periods)

For each subject, IP exposure in combined periods is the sum of the IP exposure in the parent study (defined above) plus the IP exposure in the OLE period (defined above).

Study Exposure Period in Months (Parent study)

For each randomized subject, study exposure period = [(EOS date in parent study – Randomization date) + 1] / 365.25 x 12

Study Exposure Period in Months (For OLE period)

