For each subject, study exposure period in OLE period = [(EOS date – enrollment date) + 1] / 365.25 x 12

Study Exposure Period in Months (For the combined parent and OLE periods)

For each subject, study exposure in combined periods is the sum of the study exposure in the parent study (defined above) plus the study exposure in the OLE period (defined above).

Reflexive Approach for LDL-C and VLDL-C

For all analyses related to LDL-C and VLDL-C, unless specified otherwise, an LDL-C reflexive approach will be used. When calculated LDL-C is less than 40 mg/dL or triglycerides are > 400 mg/dL, the ultracentrifugation (UC) LDL-C value and UC VLDL-C value from the same blood sample will be used instead, if available.

Two Consecutive LDL-C Values < cutoff (25 mg/dL and 40 mg/dL) The algorithm for defining the 2 consecutive LDL-C values < 25 mg/dL / 40 mg/dL separated by at least 21 days within OLE study period is summarized below:

- 1) For each blood sample draw date that has at least one LDL-C value within OLE study period, identify the lowest LDL-C value
 - a. If UC values exist regardless of the presence of calculated LDL-C values, the lowest UC LDL-C value will be used
 - b. If only calculated LDL-C values exist, the lowest calculated LDL-C value will be used
- 2) If a subject has 2 consecutive (separated by at least 21 days) LDL-C values that are < 25 mg/dL / 40 mg/dL within OLE study period, then the subject will be considered as a subject with two consecutive LDL-C values < 25 mg/dL / 40 mg/dL within OLE study period.

Two consecutive LDL-C in the parent study has been defined and derived in the same way as above.

6. Analysis Sets

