9.5 Efficacy Analyses

Table 9-1. Endpoint Summary Table

Endpoint	Primary Summary (Long-Term Safety Analysis Set and OLE Safety Analysis Set)
Primary Endpoint	
Treatment emergent adverse events 
• Adverse events• Serious adverse events• Fatal adverse events• AEs leading to withdrawal from IP• Device-related adverse events• Disease related events	Subject incidence and exposure adjusted subject incidence rate
Secondary Endpoints	
Percent change of LDL-C from baseline	Summary statistics at each scheduled visit
Achieving an LDL-C level < 40 mg/dL	Summary statistics at each scheduled visit
Exploratory Endpoints	
Change and percent change from baseline 
• non-HDL-C• ApoB• Total cholesterol• Lp(a)• Triglycerides• HDL-C• LDL-C• VLDL-C• ApoA1	Summary statistics at each scheduled visit

Endpoint	Primary Summary (Long-Term Safety Analysis Set and OLE Safety Analysis Set)
Subject incidence of events positively reviewed by the CEC: 
○ All deaths
▪ Cardiovascular death▪ Non-cardiovascular death▪ Undetermined Cause of death○ Cardiovascular events of interest:
▪ Myocardial Infarction (MI)▪ Coronary revascularization▪ Hospitalization for unstable angina▪ Heart failure▪ Cerebrovascular Events▪ Coronary heart disease death	Subject incidence of events positively reviewed by the CEC

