9.5.1 Analyses of Primary Endpoint

The current Medical Dictionary for Regulatory Activities version at the time of data lock will be used to code all adverse events (AEs) and disease related events to a system organ class and a preferred term.

Treatment-emergent adverse events are events with an onset after the administration of the first dose of investigational product as defined in [Section 5.3](#).

The subject incidence and exposure-adjusted subject incidence rate of all treatment-emergent adverse events, serious adverse events, fatal adverse events, adverse events leading to withdrawal of evolocumab, device-related adverse events, and disease-related events will be tabulated by system organ class (SOC), high level term (HLT), and preferred term (PT) in alphabetical order for the overall OLE study period using the OLE safety analysis set. These events will also be presented by yearly subject exposure time intervals. All adverse event summaries for the primary analysis of the primary endpoint will include all treatment-emergent events reported on the Event eCRF, including CEC reviewed events and disease related events.

The analyses described above (subject incidence, exposure-adjusted subject incidence rate) will also be performed combining data from the OLE study and the **parent** study

using the **OLE safety analysis set** and also be analyzed separately for the subgroup of subjects who were randomized to and received evolocumab group in the parent study with ≥ 7 years of the combined exposure for evolocumab across the parent and OLE study. Events from **parent** study classified as Target IP TEAEs will be included (adverse events occurring from the first dose of IP date to 30 days after the last dose of IP date or EOS, whichever occurs first). Disease-related events from the OLE study will be reclassified as adverse events and positively reviewed events from the OLE study will not be included to remain consistent with **parent** study adverse event reporting. This analysis will be presented by the **randomized treatment in the parent study**.

Subject incidence of treatment emergent and serious adverse events occurring in at least 1% of the subjects by preferred term will be provided in descending order of frequency for the overall OLE study period only **and combined parent and OLE study periods**.

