Appendix A. Analytical Study Week Assignments

Selected endpoints will be summarized by scheduled study visits in descriptive analyses. Since the actual visits may not exactly coincide with their scheduled visit day, the actual visit day is mapped to the study visit generally by non-overlapping consecutive intervals covering the entire time continuum. The mapping intervals for all distinct schedules are summarized in the following table.

If there is more than one record in a given analytical window, the analytical record for that scheduled visit will be defined as the record closest to the scheduled visit day ($7 \text{ days} \times \text{Number of Study Weeks} + 1$) for that scheduled visit. If two records are equidistant from the scheduled visit day, then the earlier record will be chosen. If there are multiple records on the same day, the last record will be used.

[figure not shown]
Analytical Study Week	Scheduled Visit Day	Vital signs Body weight Laboratory (lipid panel, ApoA1, ApoB, Lp(a), and serum pregnancy)	Concomitant therapy	Physical exam
Week 12	85	(1, 126]	(1, 126]	
Week 24	169	(126, 252]	(126, 252]	
Week 48	337	(252, 420]	(252, 420]	
Week 72	505	(420, 588]	(420, 588]	
Week 96	673	(588, 756]	(588, 756]	
Week 120	841	(756, 924]	(756, 924]	
Week 144	1009	(924, 1092]	(924, 1092]	
Week 168	1177	(1092, 1260]	(1092, 1260]	
Week 192	1345	(1260, 1428]	(1260, 1428]	
Week 216	1513	(1428, 1666]	(1428, 1596]	
Week 240	1681		(1596, 1750]	
Week 260	1821	(1666, EOS]	(1750, 1836]	> 1
EOS	1851		> 1836	

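### SAP 9.6.1 lets LDL-C samples drawn after evolocumab has stopped, and after adverse-event counting has closed, decide which low-LDL-C row a subject is in; an on-treatment limit is a cheap improvement

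*SAP*

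**What the plan says.** **Grouping rule.** SAP 9.6.1: "The safety analyses (TEAE and serious TEAE) will be summarized for subjects with any postbaseline LDL-C and all postbaseline LDL-C with the cutoffs of" <25, <40 and ≥40 mg/dL, for the OLE study period in the OLE safety analysis set. A further grouping needs two consecutive low values at least 21 days apart. Its algorithm in SAP 5.3 begins "For each blood sample draw date that has at least one LDL-C value within OLE study period, identify the lowest LDL-C value". Neither rule mentions treatment status or the date of event onset.

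**Sampling after stopping.** SAP 3.1: "Subjects ending administration of evolocumab should continue study assessments until the end of study". Protocol 7.2.2 says of a subject "unable to tolerate evolocumab, that subject will discontinue evolocumab but will continue to return for all other study procedures and measurements through the EOS". In SAP Appendix A "the actual visit day is mapped to the study visit generally by non-overlapping consecutive intervals covering the entire time continuum", and the last lipid window (week 260) runs to EOS with no on-drug condition.

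**Event window.** SAP 5.3 counts events as treatment-emergent "up to the EOS/Safety Follow-up visit or 30 days after the last administration of evolocumab, whichever is earlier".

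**Measures.** SAP 9.5.1 tabulates "The subject incidence and exposure-adjusted subject incidence rate of all treatment-emergent adverse events, serious adverse events, fatal adverse events" and other categories. SAP 9.6.1 does not say whether both measures apply to its rows. Table 9-1 lists "AEs leading to withdrawal from IP" as a category of its own.

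**Day 1.** Baseline is the parent-study value (SAP 5.1), so a literal reading of postbaseline takes in the pre-dose OLE Day 1 sample. Appendix A's first lipid window, (1, 126], suggests it is excluded, but 9.6.1 does not cite that window.

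**The concern.** Safety at LDL-C below 40 mg/dL is part of the rationale (Protocol 2.3), and the effects of treatment in subjects who reach that level are a secondary objective (Protocol 1.2). SAP 9.6.1 is the only section that sets adverse events against attained LDL-C. The subgroups in SAP 4.2 use baseline LDL-C, and SAP 9.5.2 reports lipid values only.

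The difficulty is that row membership can be settled by information that arises after the events in the row, and partly because of them. A subject with consistently low LDL-C who stops evolocumab for an adverse event, and later has an off-drug value of 40 mg/dL or more, leaves 'all <40' and takes that event along. Subjects who stop also have shorter event windows, which affects crude percentages differently from rates. A reader of the finished table could not separate these effects.

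**Working it through.** **1. The plan's own figure.** The only sample-size figure is the 95% interval width at n = 1600 (SAP Table 3-1). The Wald formula 2 × 1.96 × √(p(1−p)/1600) gives 0.975 points at 1% and 2.136 at 5%, as printed; all eight rows match. The point here does not depend on it.

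**2. Off-drug samples.** Protocol Table 3 schedules 11 lipid samples after Day 1: weeks 12, 24, 48, 72, 96, 120, 144, 168, 192, 216 and 260.

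| Last dose at week | Samples still to come | Of these, after last dose + 30 days |
|---|---|---|
| 48 | 8 of 11 | 8 |
| 96 | 6 of 11 | 6 |
| 144 | 4 of 11 | 4 |

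One of these at or above 40 mg/dL moves the subject out of 'all <40' and into 'any ≥40'.

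**3. Overlap of the 'any' rows.** A subject with one value on each side of 40 is in both. Overlap = 1 − P(all <40) − P(all ≥40). The documents give no LDL-C distribution, so the inputs are assumed, with k = 11:
- Independent samples, P(<40) = p: 1 − p¹¹ − (1−p)¹¹ = 0.686 at p = 0.9 and 0.999 at p = 0.5.
- Beta-binomial with mean m and within-subject correlation ρ, where a = m(1/ρ − 1) and b = (1−m)(1/ρ − 1): P(all <40) = B(a+11, b)/B(a, b) and P(all ≥40) = B(a, b+11)/B(a, b). For m = 0.9, ρ = 0.7: 1 − 0.811 − 0.036 = 0.153 (245 of 1600). For m = 0.5, ρ = 0.3: 1 − 0.069 − 0.069 = 0.862 (1379 of 1600).

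The range is therefore 15% to nearly 100%. 'Any <40' with 'all ≥40', and 'all <40' with 'all ≥40', are disjoint by definition.

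**4. Illustrative effect on rates.** Simulation, 200,000 subjects per scenario, visits as in Table 3 (±2 weeks, 5% of samples missed), event window and person-time as in SAP 5.3 and 5.1. Assumed:
- on-drug LDL-C log-normal, median 30, 35 or 40 mg/dL, between-subject log SD 0.5, within-subject 0.25 or 0.45; off-drug median 90
- evolocumab discontinuation 5% or 10% per year; study exit 2% per year
- first serious event 0.10 per year, gamma frailty variance 0.5
- 0%, 5% or 15% of serious events stop evolocumab

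Results for a true rate ratio of 1.0:

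| Serious events that stop evolocumab | 'all <40' / 'all ≥40', all OLE samples | 'any <40' / 'all ≥40', all OLE samples | Crude 'all <40' minus 'all ≥40', points | 'all' / 'all', on-treatment samples |
|---|---|---|---|---|
| 0% | 0.97–1.01 | 0.98–1.01 | +5 to +14 | not listed |
| 5% | 0.85–0.94 | 0.89–0.97 | +3 to +11 | 0.94–1.02 |
| 15% | 0.69–0.84 | 0.76–0.92 | 0 to +7 | 0.89–1.00 |

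At 15%, consider the serious-event cases who qualify for 'all <40' on their on-treatment values. Off-drug values remove 91–95% of those who stopped for the event, against 13–28% of the others. With on-treatment samples the null crude gap is −0.5 to +5 points.

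Two further runs under the same or similar assumptions gave 'all' / 'all' ratios of 0.94–1.02, 0.83–0.94 and 0.64–0.86 at 0%, 5% and 15%. With event rates of 0.05–0.20 per year, or off-drug medians of 80–100, the 15% ratio is 0.68–0.89.

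**5. Against chance at n = 1600.** The factor is exp(1.96√(1/e₁ + 1/e₂)), with 36–164 expected events in 'all <40' and 29–125 in 'all ≥40'. Taken scenario by scenario it is 1.31–1.53 either way. As factors, the distortion is 1/0.94 to 1/0.85 = 1.06–1.18 at 5%, and 1/0.84 to 1/0.69 = 1.19–1.45 at 15%. It is below random error at 5% and comparable with it at 15%.

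**The case against.** The strongest reply is that the plan makes no low-versus-high comparison. SAP 9.6.1 summarizes, SAP 9.1 rules out inference, and results are shown by parent-study group and overall, so every ratio above is a construct put on the table. That stands: no error rate or sample size is affected, and the weight is limited. It does not remove the point, because rows set side by side will be read side by side, and a row whose membership depends on later off-drug values is hard to interpret even alone.

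Second, the distortion of rates needs event-driven stopping, for which the documents give no rate; without it the ratio barely moves. That stands too. AEs leading to withdrawal are tabulated (SAP 9.5.1), so their frequency will be visible, but not by LDL-C row. SAP 8.4 provides for reporting sensitivity analyses if they prove necessary, but specifies none here.

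Third, an on-treatment limit is only a partial cure. At 15% stopping, 'any <40' against 'all ≥40' moves only from 0.76–0.92 to 0.82–0.95. That is correct; the gain for 'all' against 'all' is larger.

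A reader might also infer that the overlap makes the table unusable. It does not, since disjoint rows are already there. Nor do events that precede the qualifying value undo the 'any <40' row: in the simulation 12–20% of its first serious events do so, but only 4–12% follow an earlier sample at or above 40, and in the rest LDL-C may already have been low.

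**Conclusion.** The point holds as a cheap improvement to a descriptive table. What follows from the text alone is that classification uses the whole OLE period, that sampling continues after evolocumab stops, that event counting does not continue beyond 30 days after the last dose, and that the two 'any' rows overlap. Any size rests on the assumed LDL-C distribution, event rate and discontinuation rates, and above all on the share of events that stop evolocumab.

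A reader might infer that the table will hide harm at low LDL-C. The documents do not support this. Event-driven stopping pulls the rate ratio down, differences in follow-up length push crude incidence up, and the net direction is unknown.

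**What to change.** In SAP 9.6.1:

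- **(a)** Classify subjects by LDL-C samples taken after the first OLE dose and within the IP exposure period already defined in SAP 5.3 (to the earlier of EOS or last dose plus 14 days for Q2W, 28 days for QM). State that the pre-dose Day 1 sample is excluded, and show subjects with no qualifying sample in a separate row.
- **(b)** Report exposure-adjusted rates, as in 9.5.1, beside crude incidence. The on-treatment limit alone does not fully remove the follow-up-length effect from percentages.
- **(c)** Footnote that 'any <40' and 'any ≥40' overlap and are not to be compared with each other.

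Two displays are optional and supportive only. One is categories updated over time by the latest on-treatment LDL-C, which show a true ratio of 2.0 as only 1.32–1.56 in the simulation. The other splits events before and after the second qualifying value in the two-consecutive groups.

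The cost is a few sentences of SAP text and modest programming on data already collected. Some bias remains when adverse events lead to stopping, and the report should say so.

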9.6.2 Vital Signs

Systolic and diastolic blood pressure and heart rate will be summarized using descriptive statistics at each scheduled visit based on the OLE Safety Analysis Set for the OLE study period.

9.6.3 Exposure to Investigational Product

Descriptive statistics will be produced to describe the exposure to investigational product for both the overall OLE study period and combined parent and OLE study periods using the OLE Safety Analysis Set.

